**Table 3: Data collection plan**

	-24 to -12 h	-12 to 0h	Device place ment 0 h		6h	12h	24h	24- 48h	48- 72h	72- 96h	96- 120h	120- 144h	144- 168h	168- 192h
Consent	x													
CFS score		x	x			x	X 12 hourly	x 12 hrly						
Pupillometry		x	x		x	x								
HRV using EKG		x	x		x	x								
Maintenance meds 		x				x	x	x	x	x	x	x	x	x
Rescue Meds 		x				x	x	x	x	x	x	x	x	X
Adverse Events						x	x	x	x	x	x	x	x	X

 No additional new Maintenance Medications are allowed for the first 12 hours after device placement. Patients may remain on Maintenance Medications they are already taking. Additional Maintenance Medication are allowed after the first 12 hours of device placement.

 Patients may continue Rescue Medications during the first 12 hours of device placement.

### Data analysis & interpretation (Overview)

**Missing data:** In general, the assumption of missing at random (MAR) will be assumed. Under this assumption, we will impute or use mixed models. A sensitivity analysis, using clinical and biological expertise will be included. **Exploratory data analysis** will include exploration of distributions and relationships of the variables, using summaries, such as correlation, plots such as Loess smooth plots, and Classification and Regression Trees (CART). To satisfy parametric assumptions, transformation of variables will be used or non-parametric tests when necessary. **Continuous data:** we will use mixed models to describe changes over time, the variance covariance matrix will be chosen to be parsimonious but to fit the data and will likely be an autocorrelation matrix. **Design justification:** Although it would be better as a pilot to randomize patients to a sham and active PENFS, the numbers would be so small (and heterogeneous) that the study would have limited information. The next step would be to evaluate the acceptability of randomization in this group of patients.

## Protocol Summary/Submission Application

*Hypothesis 1:* The number approached and consented will be tracked. Reactions/ adverse events will be summarized and reasons for early termination, if any, evaluated.

*Hypothesis 2a, 2b:* The scoring tool will be adapted for the appropriate age range of the patient (Table 2). We aim for at least 80% scoring ( $\geq 8/10$  scheduled scoring per protocol while the device is worn). The association of the score and the number of doses of maintenance and rescue medications will be summarized with a spearman correlation and exact 95% Confidence intervals (CI).

*Hypothesis 3a:* HRV and Pupillometry measures will be tracked over time with any loss of data recorded with reasons. Wilcoxon Rank Sum test will be used to compare the mean  $\pm$ SD for the parameters for the 12-hour periods before and after device placement.

*Hypothesis 3b:* The number of doses of maintenance and rescue medications for control of PSH symptoms will be compared to historic data using a t-test or non-parametric Mann Whitney. Further a classification tree will be used to evaluate the effect of demographics, clinical history and use of PENFS.

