
Aim 1: Demonstrate the feasibility of use of PENFS to treat PSH, and tolerability of the device. Hypothesis: The PENFS device will be well tolerated, defined as < 10% early termination from the study. We will recruit 20 patients with ASBI and PSH who will receive PENFS therapy.
 
Aim 2a: Evaluate the feasibility of capturing pediatric PSH symptoms using the CFS scoring tool. Hypothesis: It is feasible to monitor the severity of PSH using a CFS scoring tool (Table 1a,1b). The scoring tool will be adapted for the appropriate age range of the patient (Table 2). We aim for at least 80% scoring (<math>\geq 8/10</math> scheduled scoring per protocol while the device is worn).
 
Aim 2b: Evaluate the effectiveness of the PENFS device in reducing PSH symptoms using change in CFS score. Hypothesis: A decrease in CFS severity score with use of PENFS will be associated with a lower number and/or doses of maintenance and rescue medications for control of PSH symptoms.
 
Aim 3a: Evaluate the change in autonomic balance with use of PENFS device Hypothesis: Heart Rate Variability (HRV) and pupillometry parameters that correspond to sympathetic and parasympathetic activity will be different after PENFS device placement compared to before, reflecting an increase in parasympathetic tone. All patients will be on routine continuous EKG monitoring in the PICU during the study period of interest. Similarly, pupillometry is routinely performed in patients with ASBI in the PICU.
 
Aim 3b: Evaluate feasibility of measuring PENFS effectiveness in treating PSH by a decrease in medication use. Hypothesis: It would be feasible to use the maintenance and rescue medication dosing and frequency as a marker of severity of PSH. PENFS device use will result in lesser number and/or doses of maintenance and rescue medications for control of PSH symptoms. We will compare the pilot sample to a historical cohort to allow power analysis and sample size calculation for a future larger efficacy trial, recognizing that this pilot study is not powered for efficacy.

D. Background, significance, and rationale (including description of preliminary studies and any results):

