**Table 2 PSH scoring modified for pediatric population**

## Protocol Summary/Submission Application

	0	1	2	3
Heart rate	1-4 years: <110 5-15 years: <100	1-4 years: 110-124 5-15 years: 100-119	1-4 years: 125-139 5-15 years: 120-139	1-4 years: ≥140 5-15 years: ≥140
Respiratory rate	1-4 years: <30 5-15 years: <25	1-4 years: 30-34 5-15 years: 25-29	1-4 years: 35-39 5-15 years: 30-34	1-4 years: ≥40 5-15 years: ≥35
Systolic blood pressure	1-4 years: <100 5-15 years: <120	1-4 years: 100-109 5-15 years: 120-129	1-4 years: 110-119 5-15 years: 130-139	1-4 years: ≥120 5-15 years: ≥140
Diastolic blood pressure	1-4 years: <65 5-15 years: <75	1-4 years: 65-72 5-15 years: 75-82	1-4 years: 73-79 5-15 years: 83-89	1-4 years: ≥80 5-15 years: ≥90
Temperature	<37°C	37-37.9°C	38-38.9°C	≥39°C
Sweating	Normal	Increased sweating	Localized diaphoresis	Generalized diaphoresis
Muscle tone increase	Absent	Mild increase	Neat increase	Generalized spasticity or opisthotonus

sympathetic (dilation velocity) and parasympathetic system (% change in pupil size, latency, constriction velocity) activity and sympatho-parasympathetic balance (baseline pupil size) (24). PSH, as the name implies, is associated with uncontrolled paroxysms of sympathetic activity that results in pupillary dilation among other symptoms. It is conceivable that an increase in parasympathetic activity would alter these parameters that could be compared using the patient as his/her own control

**PENFS device – description, mechanism of action, and applications** The PENFS (auricular

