### **Aim 3a: Evaluate the change in autonomic balance with use of PENFS device**

**Methods:** We will use two separate validated modalities to evaluate the autonomic activity/balance in response to use of the device – HRV and Pupillometry. HRV denotes the beat-to-beat variability in the R-R interval on the EKG. Cardiac pacemaker automaticity is continuously altered and regulated by the autonomic nervous system (ANS). The parasympathetic system regulates HR on a beat-to-beat basis whereas the sympathetic system has slower onset but longer duration of action (16-18). Decreased HRV parameters has been shown to be associated with increased 30-day mortality in critically ill patients (19). Children with PSH were shown to have significant differences in HRV parameters compared to controls (20). We will calculate time-domain (mean heart rate, standard deviation of all average R-R intervals (SDNN), root mean square of the successive differences (RMSSD), physical stress index (PSI), approximate entropy (ApEn); successive R-R interval difference (SRD)) and frequency-domain indices (total power (TP), high frequency (HF), low frequency (LF), normalized HF, normalized LF, and LF/HF ratio) and compare the 12-hour period before and after placement of the PENFS device. Three separate 5-minute segments of continuous EKG tracings at rest (lying in bed) and body temperature 36-37.5C will be identified for both periods for comparison. Similarly, we will compare the pupillometry parameters along with direction of change before and after device placement.

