**D. Describe procedures to be employed in analyzing data (including a power analysis):**

*This is a pilot feasibility study of use of the device. A convenience sample of 20 patients was chosen.*

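### Hypothesis 3a names an unpaired test, the Wilcoxon rank-sum, for a before/after comparison in the same children

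*Combined protocol and SAP*

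**What the plan says.** Aim 3a expects that HRV and pupillometry parameters "will be different after PENFS device placement compared to before". The Aim 3a methods compare the 12-hour periods on either side of device placement in the enrolled children. The background on autonomic measurement argues that a rise in parasympathetic activity would alter "these parameters that could be compared using the patient as his/her own control".

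For the test itself, the Hypothesis 3a paragraph says the "Wilcoxon Rank Sum test will be used to compare the mean" ± SD of the parameters for the two periods.

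Three other places bear on this:

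- Under Continuous data, the analysis overview says "we will use mixed models to describe changes over time". Hypothesis 3a does not refer to it.
- The Aim 3a methods take "Three separate 5-minute segments of continuous EKG tracings at rest (lying in bed") in each period. Table 3 marks both HRV and pupillometry at −12 to 0 h, 0 h, 6 h and 12 h. No section says how these readings become one value per child per period.
- Section 6, item D, on sample size: "A convenience sample of 20 patients was chosen". No significance level, effect size, correlation or power is given for Aim 3a.

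**The concern.** The rank-sum test treats the before values and the after values as coming from two separate groups of children. Here every child supplies both. The data collection section lists no HRV or pupillometry for the historical cohort, so the Aim 3a contrast can only be within-child. No section names a paired test for it.

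Ignoring the pairing gives the wrong standard error for the contrast. If a child's two values are positively correlated, as the own-control rationale supposes, the p-values come out too large and a real change can be reported as absent. If they are negatively correlated, the p-values are too small.

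The sentence has two further gaps. A rank test does not compare means ± SD, so the test and the stated summary do not match. And because no rule reduces each period to one value per child, an analyst could enter repeated readings as if they were separate children, which pushes the error the other way.

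**Working it through.** **Plan's own figure.** There is nothing to reproduce: 20 is a convenience sample and no power is claimed.

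**Inputs.** From the documents: 20 children (Section 6, item D), one before and one after period per child, three HRV segments per period (Aim 3a methods). Assumed, because the documents are silent: two-sided 5% level, normal data, within-child correlation ρ, and shift d in between-child SD units.

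**Step 1: type I error by formula.** With equal variances, the variance of the difference in means is 2σ²(1 − ρ)/n. An unpaired test uses 2σ²/n. Its true size is therefore about 2 × [1 − Φ(1.96/√(1 − ρ))]:

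- ρ = 0: 1.96/1 = 1.96, size 5.0%
- ρ = 0.3: 1.96/√0.7 = 2.34, size 1.9%
- ρ = 0.5: 1.96/√0.5 = 2.77, size 0.6%
- ρ = −0.3: 1.96/√1.3 = 1.72, size 8.6%

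**Step 2: simulation of the two rank tests.** This used 20 bivariate-normal pairs and 20,000 replicates per setting, comparing the rank-sum test (normal approximation, continuity-corrected) with the exact signed-rank test. Each cell shows rank-sum / signed-rank.

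| ρ | Type I error | Power, d = 0.5 | Power, d = 0.8 |
|---|---|---|---|
| −0.3 | 8.5% / 4.9% | 34% / 25% | 65% / 53% |
| 0 | 5.0% / 5.0% | 32% / 31% | 67% / 65% |
| 0.3 | 2.0% / 4.7% | 29% / 42% | 70% / 80% |
| 0.5 | 0.8% / 4.7% | 27% / 54% | 72% / 91% |
| 0.7 | 0.15% / 4.5% | 23% / 76% | 77% / 99% |
| 0.8 | 0.03% / 4.8% | 22% / 90% | 81% / 100% |

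Relative power loss at d = 0.5 is nil at ρ = 0. At 0.3 it is (41.5 − 29.3)/41.5 = 29%, and at 0.5 it is (54.3 − 27.2)/54.3 = 50%. At d = 1.0 the loss is small: 89% vs 94% at ρ = 0.3, 92% vs 99% at 0.5, and 95% vs 100% at 0.7.

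**Step 3: conditional case, HRV segments entered as 60 vs 60 independent values.** Take total variance 1, with segment variance 0.3 and the remaining 0.7 split between child and child-by-period. Segments within a child-period then correlate 0.7, which inflates variance by 1 + 2 × 0.7 = 2.4. The child-period mean has variance 0.7 + 0.3/3 = 0.8, so before and after means correlate r = (child variance)/0.8. The approximate size is 2 × [1 − Φ(1.96/√(2.4(1 − r)))]. The simulation used 10,000 replicates.

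| Child variance | r | Formula | Simulated |
|---|---|---|---|
| 0 | 0 | 20.6% | 19.9% |
| 0.2 | 0.25 | 14.4% | 15.1% |
| 0.3 | 0.38 | 11.0% | 11.8% |
| 0.4 | 0.50 | 7.4% | 7.6% |
| 0.5 | 0.62 | 3.9% | 4.5% |
| 0.6 | 0.75 | 1.1% | 1.7% |

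By the formula, size crosses 5% at r = 1 − 1/2.4 = 0.58. Signed-rank on child means stayed between 4.5% and 5.2% in all 12 variance splits simulated, which include these six.

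**The case against.** The best reply is that this is a slip of the pen. Hypothesis 3b uses the name Mann-Whitney for the comparison with historical patients, while 3a uses Wilcoxon for the before/after one. Two names for the same unpaired test in adjacent paragraphs suggest that signed-rank was meant in 3a. That is plausible but cannot be settled from the documents, and an analyst following the text would run the wrong test. It makes the correction easier, not unnecessary.

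Second, the overview already plans mixed models for continuous data, and a model with a child effect would respect the pairing. This stands in part: the plan does contain a suitable method. But the paragraph written for Hypothesis 3a names a different one, so the two must be reconciled.

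Third, the harm is conditional and modest. At zero correlation nothing is lost, and at a 1.0 SD shift little is. Aim 3a has no success threshold, and Aim 3b says that the pilot is not powered for efficacy. All of this stands and limits the weight of the point.

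Fourth, nothing says that segments will be entered as independent observations, and the variance splits in step 3 are assumed. That also stands. Step 3 shows why a summary rule is needed; it does not predict what will be done and adds nothing to the seriousness of the point.

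**Conclusion.** The concern holds. As written, Hypothesis 3a applies a test for independent groups to paired data, and should be corrected before analysis. With one value per child per period, the rank-sum p-values are calibrated only at zero within-child correlation. At positive correlation they are conservative: actual type I error falls to 2.0% at 0.3 and 0.8% at 0.5, and about half the power for a 0.5 SD shift is lost at a correlation of 0.5. At negative correlation they are liberal.

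These figures assume 20 complete pairs, normal data and a two-sided 5% level; the correlation and shift are not in the documents. The consequence is a possibly missed or misreported autonomic signal in the pilot's results. No decision rule is affected.

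**What to change.** Replace the test sentence in Hypothesis 3a with text that does three things:

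1. **Define one before and one after value per child for each parameter.** For HRV, use the mean of the three segments in each period, and say how those segments relate to the Table 3 time points. For pupillometry, state which readings belong to each period, including the 0 h reading, and how they are combined.
2. **Name the Wilcoxon signed-rank test on the within-child differences.** Alternatively, name the overview's mixed model with a child random effect as the Hypothesis 3a analysis.
3. **Report the within-child change with a 95% CI in place of the comparison of mean ± SD.** With signed-rank, the matching estimate is the Hodges-Lehmann pseudomedian, which equals the median change if the differences are symmetric.

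The cost is one or two sentences of analysis text for the test, plus the summary rule, and no new data. There is one trade-off. Signed-rank drops any child missing either period, and the plan expects some loss: "HRV and Pupillometry measures will be tracked over time with any loss of data recorded with reasons". The mixed model keeps those children, but relies on missing at random and on its model assumptions with about 20 children.

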### **E. Design and methods (including experimental design, technical details and laboratory methodology):**

#### **Design & Methods**

In this prospective unblinded pilot study we will enroll eligible patients until 20 parent/child dyads complete the study. It is expected many of the consented patients will not meet the eligibility criteria of CFS score > 6 (moderate severity of PSH). Those children will be considered Screen Failures and their parents/LAR told they are ineligible to continue in the study. Children admitted to the PICU at CW aged 2-17 years with ASBI and symptoms of PSH with a CFS score > 6 (moderate severity of PSH) will be eligible for inclusion. Exclusion criteria include age < 2 years (small ears thus less surface area to apply the leads), ear deformity or severe dermatitis of ear lobes, intractable seizures, heart block, patients with other implantable devices (cardiac pacemaker, vagal nerve stimulator, etc.) or known pregnancy.

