### **Aim 2a: Evaluate feasibility of scoring PSH symptoms using the PSH scoring tool**

**Methods:** The CFS (Table 1a) will be used to score the severity of PSH using the pediatric adaptation for the appropriate age range (Table 2 – diastolic blood pressure will not be used for scoring). CFS scoring will be performed by the bedside nurse who will be trained in using the scoring tool. PSH severity for the 12-hour period prior to placement of the device will be calculated retrospectively based on the features of CFS. After placement of the device, patients will be scored prospectively every 12 hours while the device is worn. The device will be discontinued after 120 hours of wear (usual duration of wear of a device). Scoring will be continued every 12 hours until 120 hours of device placement and then for another 72 hours (total of 192 hours for complete study duration). Every CFS score will be based on the severity of PSH symptoms in the preceding 12 hours.

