### **Aim 3b: Evaluate feasibility of measuring PENFS effectiveness in treating PSH by a decrease in medication use**

**Methods:** The maintenance medications and the number of doses and type of rescue medications administered will be collected for every 24 hours (0-24h, 25-48h, 49-72h, 73-96h, 97-120h, 121-144h, 145-168h, 169- 192h) for the enrolled patients. These will be compared to a historical cohort of PSH patients. The historical cohort will consist of PSH patients (2-17 years old) identified using the ICU Neurology administrative dataset from January 2018 – August 2021. This dataset will be used to identify ASBI patients who likely developed PSH. Eligible patients with PSH will be identified and relevant data collected by individual chart review. During this period all the PSH patients were followed by ICU Neurology thus ensuring a uniform approach to their treatment. We have also developed a practice guideline for treatment of PSH that will ensure uniform treatment of these patients during the study period. Similar to Aim 2a, we will examine the need for additional maintenance medications or change in frequency of rescue medications with discontinuation of the device. We hypothesize that, with discontinuation of the device, the patients may experience worse PSH symptoms as demonstrated by increasing CFS score and need for additional maintenance and/or rescue medications.

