## Protocol Summary/Submission Application

complete the study. If the patient does meet CFS scoring criteria for study enrollment, we will collect the CFS score for a 12-hour period before placement of the device followed by every 12 hours while the device is in place and for an additional 72 hours after removal of the device.

**Data collection & Management:** We will collect demographics, cause of ASBI, imaging findings, sedative, pain and other neurotropic medications, and maintenance and rescue medications for PSH including their number and doses for every 24-hour period from placement of the device. We will also collect all the HRV and pupillometry parameters for the 12-hour period before and after placement of the device. For the historical cohort, we will collect demographics, cause of ASBI, imaging findings, maintenance and rescue medications used in each 24 hour period for the first 120 hours and then additional 72 hours from the time of meeting CFS score > 6 criteria. . The REDCap database for this study will be developed and managed by Quantitative Health Sciences on MCW-secure servers

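### Aim 3b compares raw dose counts with a historical cohort but sets no time window, no observed-time denominator and no rule for partial follow-up

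*Combined protocol and SAP*

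**What the plan says.** The statistical text for this aim is the Hypothesis 3b paragraph under Data analysis & interpretation: "The number of doses of maintenance and rescue medications for control of PSH symptoms will be compared to historic data using a t-test", with Mann-Whitney as the alternative. It adds: "Further a classification tree will be used to evaluate the effect of demographics, clinical history and use of PENFS". Neither sentence mentions hours on device or hours observed.

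The Aim 3b methods describe collection. Medication data "will be collected for every 24 hours (0-24h, 25-48h, 49-72h, 73-96h, 97-120h, 121-144h, 145-168h, 169- 192h) for the enrolled patients", and then "These will be compared to a historical cohort of PSH patients". Under Aim 2a, "The device will be discontinued after 120 hours of wear", and follow-up runs a further 72 h. For the period after removal, the Aim 3b methods state: "We hypothesize that, with discontinuation of the device, the patients may experience worse PSH symptoms as demonstrated by increasing CFS score", together with a need for more medication.

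For the historical cohort, Data collection & Management takes medications "used in each 24 hour period for the first 120 hours and then additional 72 hours from the time of meeting CFS score" above 6. Device children are timed from placement, which the Aim 1 methods allow up to 24 h after that score is met.

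On the sample, Design & Methods says "we will enroll eligible patients until 20 parent/child dyads complete the study". No completion or minimum-stay condition is given for historical children. Section 7, item A, ends data collection when a subject withdraws.

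**The concern.** A dose count means little without the time over which it was accumulated. Here that time can vary in three ways.

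- **Device status.** Five of the eight 24 h bins are on device and three are off, and the plan predicts opposite movements in the two parts. The size of the cohort difference depends on which bins enter it, and the plan does not say.
- **Length of observation.** Read literally, a child seen for 48 h enters a comparison of counts as a child who needed few doses.
- **Recruitment.** The device sample is topped up until 20 dyads complete, and nothing comparable applies to the historical cohort. Length of observation may therefore differ between cohorts for reasons unrelated to the device.

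The aims section says the pilot is not powered for efficacy. It also says that this comparison is to feed the power and sample size calculation of a later trial, so an ambiguous estimate would carry forward.

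**Working it through.** **Inputs from the documents:** 120 h on device, 72 h after removal, 24 h bins, 20 completers, hypothesised dropout of at most 10%. **Assumptions, not in the documents:** a 30% on-device reduction, a 20% rise after removal, a halving of the dose rate after 120 h, exit fractions and exit times.

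**1. The plan's own figure.** 120 + 72 = 192 h, which agrees with the stated study duration. 192/24 = 8 bins, 5 on device and 3 off. On-device share = 120/192 = 0.625.

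**2. Dilution if all bins are summed and the effect ends at removal.**

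- Constant dose rate: 0.30 × 120/192 = 18.75%, about 19%.
- Rate halves after 120 h in both cohorts (Section 2, item A, describes early severity followed by weaning): control total = 120 + 0.5 × 72 = 156 units; difference = 0.30 × 120 = 36 units; 36/156 = 23%.
- Constant rate with a 20% rise after removal: (0.30 × 120 − 0.20 × 72)/192 = 21.6/192 = 11.25%.

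**3. Early exit from one cohort, identical treatment.** With exit fraction f, the proportional fall in the mean 192 h count is:

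| Exit pattern | Formula | f = 10% | f = 20% |
|---|---|---|---|
| Uniform over 0-192 h, constant rate | 0.5f | 5% | 10% |
| All at 48 h, constant rate | f(1 − 48/192) = 0.75f | 7.5% | 15% |
| All at 48 h, rate halves after 120 h | f(1 − 48/156) = 0.69f | 6.9% | 13.8% |

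If the exits were historical, uniform in time and unrelated to need, the device/historical ratio with no true effect would be 1/(1 − 0.5f): 1.05 at 10% and 1.11 at 20%. The device would look worse. Exits related to need, such as death or early recovery, could act either way.

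**4. Replacement.** At 10% dropout, 20/0.90 = 22.2, so 23 children are needed for 20 completers, and about 3 early exits would be replaced on the device side.

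**5. Simulation check.** Assumed: 20 device and 40 historical children, 4 doses a day, gamma-Poisson counts with shape 1.5, uniform exit times, no effect off device, 2,000 replicates.

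- No exits, on-device ratio 0.70: raw 192 h totals give a median ratio of 0.82; the 0-120 h rate gives 0.705.
- 20% historical exits, no effect: raw totals give 1.11 and Mann-Whitney rejects in 7% of replicates; the rate gives 0.99 and rejects in 4.5%.

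**6. Effect on the later trial.** If the standardised difference falls to 0.625 of its on-device value with SD unchanged, the sample size rises by 1/0.625² = 2.56. For a true difference of 0.8 (two-sided 5%, 80% power), 2(1.96 + 0.84)²/0.8² gives 25 per arm. At 0.8 × 0.625 = 0.5 it gives 63.

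**The case against.** The strongest reply is that the plan leaves room for a sound analysis. Both cohorts are recorded in 24 h bins with the same 120 h + 72 h layout. The Aim 3b methods look at discontinuation separately, and the general analysis text offers mixed models over time, a missing-at-random approach and a sensitivity analysis. A 0-120 h or per-day comparison would fit these words. That stands as far as it goes: the bins make the right analysis possible. They do not say which bins are compared, and the general text is not tied to Hypothesis 3b, for which a two-sample test of counts is named.

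A reader might infer several stronger things that the documents do not support:

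- *That the effect is diluted by design.* No section sums doses over 192 h. The dilution is conditional on that choice.
- *That children who stop early are dropped.* The completion wording is a recruitment target. No text excludes them from analysis, and reasons for early termination are to be evaluated.
- *That testing each bin gives a 56% chance of a false positive.* 8 bins × 2 drug classes = 16 tests and 1 − 0.95^16 = 56%, but this needs independent tests. Repeated bins in the same children will be correlated, and bin-wise testing is not stated.
- *That end-of-life dosing inflates the historical count.* The documents describe no deaths or redirection of care, the count is limited to doses given for PSH, and such doses could occur in either cohort.
- *That doses will be imputed after death.* The general missing-data text does not prescribe this; it simply does not rule it out.

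**Conclusion.** The gap is real and should be closed before analysis. Hypothesis 3b tests a raw count without fixing the window, the denominator or the treatment of partial follow-up, and an analyst could defend several different answers from the same data.

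The size is moderate and conditional. A 30% on-device reduction would be reported as about 19-23% if bins are summed and the effect ends at removal. Early exit by 10-20% of one cohort shifts that cohort's mean count by 5-15%, depending on exit times. These figures rest on assumed effects, dose profiles and exit rates.

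The net direction cannot be read from the documents. Dilution pulls towards no difference, and exits may act either way. The later clock start in device children, combined with early severity, would tend to favour the device. The consequence is limited to the pilot's effect estimate and the later sample size, since no efficacy claim is planned.

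**What to change.** Rewrite the Hypothesis 3b paragraph to state the following.

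1. **Comparison.** Doses per observed 24 h over 0-120 h. Use either a count model (for example negative binomial) with log observed hours as offset, or the planned test applied to each child's rate. Choose one in advance. A model with child random effects and cohort-by-period terms is more than 20 device children are likely to support.
2. **Outcomes.** Keep maintenance and rescue doses separate. New maintenance drugs are barred for the first 12 h after placement, so that count partly reflects a protocol rule.
3. **After removal.** Report 120-192 h separately.
4. **Population.** Every child in whom a device was placed, whether or not the dyad completes.
5. **End of observation.** One rule for both cohorts (death, comfort care or discharge), with no doses imputed after death.
6. **Clock.** State the start for each cohort, CFS above 6 or placement, and report how the result changes when they are aligned.

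A rate does not remove everything. With front-loaded dosing, a child who leaves early contributes only the heavier days. A descriptive table of doses by 24 h bin, with the number of children under observation in each, would show this.

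The cost is a reworded paragraph, exit times recorded for both cohorts and slightly more analysis work. The bins are already collected.
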